3.4. DLT Definition

Severity of AEs will be graded according to CTCAE v 4.03. AEs meeting the following definition occurring in the first two cycles of treatment (up to 28 days post second dose) which are not related to progressive disease and attributable to PF-05082566 alone (Portion A) or to PF-05082566 in combination with rituximab (Portion B) will be classified as DLTs:

Hematologic:

- Grade 4 neutropenia [absolute neutrophil count (ANC) $<500/\text{mm}^3$ or $<0.5 \times 10^9/\text{L}$] lasting >7 days;
- Febrile neutropenia (defined as neutropenia \geq Grade 3 [ANC $<1000 \text{ cells}/\text{mm}^3$] and a body temperature $\geq 38.5^\circ\text{C}$);
- Neutropenic infection (ANC $<1,000/\text{mm}^3$ or $<1.0 \times 10^9/\text{L}$, and Grade >3 infection);
- Grade ≥ 3 thrombocytopenia ($<50,000 - 25,000/\text{mm}^3$ or $<50.0 - 25.0 \times 10^9/\text{L}$) with bleeding;
- Grade 4 thrombocytopenia ($<25,000/\text{mm}^3$ or $<25.0 \times 10^9/\text{L}$) >3 days;
- Grade 4 anemia (hemoglobin $<6.5 \text{ g/dL}$ or 4.0 nmol/L);
- Grade ≥ 3 hemolysis ($>2 \text{ gm}$ decrease in hemoglobin requiring medical intervention [transfusion or steroids]).

Non-Hematologic:

- Grade ≥ 3 toxicities, except those grade 3 events that respond to treatment (eg, grade 3 nausea, vomiting, diarrhea that responds to standard medical supportive care within 48 hours would not be considered a DLT).

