Each patient will initially receive the first dose on Cycle 1 Day 1 with a 28-day observation period. Cycle 2 Day 1 will start on Day 29. After completion of Cycle 2, patients will be asked to sign an additional consent document for confirmation of the patient's willingness to continue participation in this study before starting Cycle 3. Patients clinically benefiting from study treatment without unacceptable toxicity, objective disease progression, or withdrawal of consent will be given the opportunity to continue treatment on a reduced visit schedule (Day 1 of each cycle), or as clinically indicated, until disease progression, unacceptable toxicity, or withdrawal of consent up to a maximum of 2 years from the first dose of study drug, or until one of the patient withdrawal criteria under [Section 6.4](#) becomes a reason to discontinue study treatment. Dose escalation will follow the 3+3 algorithm described in [Section 3.3.1](#).

Patients discontinuing from the study before the second dose is given (Cycle 2 Day 1) for reasons other than treatment-related toxicity will be replaced in order to complete the cohort and have an adequate assessment.

Patients that discontinue from the study after the completion of second dose of therapy for reasons other than treatment-related toxicity will be discussed on a per patient basis between the sponsor and the investigator in terms of whether the patient requires replacement or can continue to be observed off study for the duration of the DLT observation period (ie, total 8 week period).

If the above replacement occurs, the patients who are lost to follow-up due to reasons unrelated to treatment related adverse events (AEs) are not evaluable for DLT. See [Section 9.1](#).

Updated safety information in non-Japanese patients indicate that PF-05082566 infusion has thus far not resulted in clinically significant infusion reactions. Therefore, there will not be a waiting period in the same dose cohort between adjacent patients.

The dosing interval may be reconsidered and amended during the study based on the emerging safety and PK^{CCI} data.

Seven (7) patients have been enrolled in the 2 cohorts described above and the 2 tested dose levels of PF-05082566 (5.0 mg/kg and 10 mg/kg) were well tolerated in patients recruited in Japan with no DLTs reported. Japanese sites are currently participating in the expansion cohort of Portion A and Portion B.

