The doses of PF-05082566 will be assigned to each enrolled patient using the modified TITE-CRM (Cheung et al., 2000).⁴ The goal of the trial is to determine the dose of PF-05082566 associated with a 25% probability of a DLT (a target DLT rate of 0.25). In Portion B, the first 3 patients (first cohort) will be treated at 0.03 mg/kg. For each subsequent patient eligible for enrollment, the probability of DLT is estimated for each level based on all the collected data from all treated patients up to that time and the prior expectations of toxicity, and the patient is assigned to the currently estimated target level (with escalation restrictions as indicated below), defined as the dose having an estimated probability of DLT closest to but not greater than the target rate (25%). The probabilities of toxicity are estimated based on a Bayesian statistical model with prior distribution (projected from the Portion A single agent data and pre-clinical data) to learn about the overall dose-toxicity relationship. Patients' DLT data will be reported to the study statistician who will update the dose-toxicity model before the next enrolled patient is treated.

In the TITE-CRM paradigm, patients who have enrolled in the trial but have not experienced DLT will be included in the probability calculation with an initial weight equal to the proportion of the 8-week (2 cycles of PF-05082566) DLT observation period the patients have completed (however the weight function may be modified if the Portion A safety data suggest different weight (toxicity) patterns in Cycle 1 and Cycle 2+ of PF-05082566, and/or accumulating safety data in Portion B suggest a different pattern); patients who experience DLT or complete the observation period without DLT will be assigned full weight (=1). Details on the TITE-CRM method are provided in [Section 9.2](#) and the Statistical Analysis Plan.

To avoid overly rapid escalation and to retain the efficiency of dose administration when enrollment is fast, the following restrictions and practical considerations will be followed.

- Dose skipping in escalation to untested doses is not allowed ($k \rightarrow k+1$). In particular, at least 3 patients should have been treated at dose level k before escalation to dose level $k+1$;

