5.4. Administration

Patients will receive doses of PF-05082566 IV once every 4weeks (1 cycle). A cycle is defined as the time from the Day 1 dose to the next Day 1 dose. If there are no treatment delays, a cycle will be 4 weeks in duration.

Premedication is recommended for all patients, and may include an antihistamine, an anti-inflammatory agent, or a pain reliever.

The duration of infusion is 1 hour (-5/+15 minutes). The infusion rate should be reduced or interrupted in the case of symptoms of infusion reaction, and symptomatic treatment administered. The infusion may be continued at one-half the previous rate upon improvement of symptoms. If symptoms persist or worsen, the infusion should be discontinued permanently.

Patients on Portion B of the study will receive doses of rituximab IV once every week for the first cycle of treatment at a fixed dose of 375 mg/m². Initiation of PF-05082566 will commence approximately 24 hours after the second weekly on study full dose of rituximab has been administered. For additional details about the administration of rituximab, refer to rituximab package insert.

Medication errors may result in this study from the administration or consumption of the wrong product, by the wrong patient, at the wrong time, or at the wrong dose strength, or administration of a study drug at the wrong study visit day. Such medication errors occurring to a study participant are to be captured on the medication error case report form (CRF) which is a specific version of the adverse event (AE) page and on the SAE form when appropriate. In the event of medication dosing error, the sponsor should be notified immediately.

Medication errors are reportable irrespective of the presence of an associated AE/SAE, including:

- Medication errors involving patient exposure to the investigational product.
- Potential medication errors or uses outside of what is foreseen in the protocol that do or do not involve the participating patient.

Whether or not the medication error is accompanied by an AE, as determined by the investigator, the medication error is captured on the medication error version of the adverse event (AE) page and, if applicable, any associated AE(s) are captured on an AE) CRF page.

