5.4.3. Dose Delays for PF-05082566

A new cycle of treatment may begin only if:

- ANC $\geq 500/\mu\text{L}$;
- Platelet count $\geq 50,000/\mu\text{L}$;
- Non-hematologic toxicities have returned to baseline or Grade ≤ 1 severity (or, at the investigator discretion, Grade ≥ 2 if not considered a safety risk for the patient).

Note: withhold scheduled dose for liver function test related AEs (including asymptomatic) Grade ≥ 3 until return to baseline or Grade ≤ 1 severity. In cases of potential liver injury, see [Section 8.5.2](#). In such cases, consultation with a hepatologist should be considered in the decision to initiate treatment with anti-inflammatory medications.

If the above conditions are not met, treatment must be delayed. If, within 8 weeks all toxicities have recovered within the limits described above, treatment with PF-05082566 can be resumed. If persisting toxicity does not allow for the resumption of treatment after 8 weeks of delay, the patient will be permanently discontinued from study treatment.

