In the TITE-CRM paradigm, patients who have enrolled in the trial but have not experienced DLT will be included in the probability calculation with a weight equal to the proportion of the 8-week (2 cycles of PF-05082566) DLT observation period the patients have completed (however the weight function may be modified if safety data suggest different weight (toxicity) patterns in Cycle 1 and Cycle 2 of PF-05082566, or an adaptive weight function if ongoing safety data suggest different toxicity patterns in Cycle 1 and Cycle 2 of PF-05082566); patients who experience DLT or complete the observation period without DLT will be assigned full weight (=1) (for details see the Statistical Analysis Plan).

[Section 3.3.2](#) describes stopping rules and some restrictions and practical considerations on dose escalation.

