In the TITE-CRM paradigm, patients who have enrolled in the trial but have not experienced DLT will be included in the probability calculation with a weight equal to the proportion of the 8-week (2 cycles of PF-05082566) DLT observation period the patients have completed (however the weight function may be modified if safety data suggest different weight (toxicity) patterns in Cycle 1 and Cycle 2 of PF-05082566, or an adaptive weight function if ongoing safety data suggest different toxicity patterns in Cycle 1 and Cycle 2 of PF-05082566); patients who experience DLT or complete the observation period without DLT will be assigned full weight (=1).

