6.5.3.4. Dose Delays

Applicable to PF-05082566 and rituximab.

Dose Delay is the difference between the actual time between two consecutive non-zero doses and the planned time between the same two consecutive non-zero doses.

PF-05082566 in Portion A

Dose delay in Cycle x (days) = Date of first dose of PF-05082566 in Cycle x – Date of first dose of PF-05082566 in Cycle (x-1) – 28, where $x > 1$.

PF-05082566 in Portion B

In Cycle 1,

Dose delay (days) = Study day of first dose of PF-05082566 – 9 [Note: Cycle 1 starts on Day -7 and the first dose of PF-05082566 is scheduled for Cycle 1 Day 1].

In Cycle x,

Dose delay in Cycle x (days) = Date of first dose of PF-05082566 in Cycle x – Date of first dose of PF-05082566 in Cycle (x-1) – 28, where $x > 1$.

Rituximab

Dose delay for Dose x (days) = Date of Dose x – Date of Dose (x-1) – 7, where $x > 1$.

Dose delays will be grouped into the following categories:

- No delay.
- 1-2 days delay.
- 3-6 days delay.
- 7 or more days delay.

For example, for PF-05082566, administered on a 4-week schedule, if one patient receives PF-05082566 on Day 1, then the next PF-05082566 administration date will be on Day 29; however, if the patient receives PF-05082566 at Day 30 or 31, this will be summarized in the 1-2 days delay category.

The number and percentage of patients with delayed study drug administration and maximum length of delay, ie, the worst case of delay if patients have multiple dose delays will be summarized.

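### The TITE-CRM weight reaches 1 after a fixed 8 weeks, but the DLT window in Protocol 3.4 closes 28 days after dose 2, so a DLT-free patient with a late Cycle 2 is credited too early

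*Protocol*

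**What the plan says.** Protocol 3.4 classifies as DLTs qualifying events "occurring in the first two cycles of treatment (up to 28 days post second dose"). The 3+3 rule in Protocol 3.3.1 uses the same end: the next level opens only after patients have been observed for 28 days following dose 2.

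The model-based rule uses a different clock. Protocol 3.3.2 enters DLT-free patients "with an initial weight equal to the proportion of the 8-week (2 cycles of PF-05082566) DLT observation period the patients have completed". Protocol 9.2 repeats this as "a weight equal to the proportion of the 8-week (2 cycles of PF-05082566) DLT observation period the patients have completed", and SAP 5.1.2 matches it. SAP 5.1.2 then adds that "patients who experience DLT or complete the observation period without DLT will be assigned full weight (=1").

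Three further provisions matter:
- Protocol 3.3.1 plans dose 2 for Day 29.
- Protocol 5.4 says "A cycle is defined as the time from the Day 1 dose to the next Day 1 dose", and that this is 4 weeks only when nothing is delayed.
- Protocol 5.4.3 requires a new cycle to wait for recovery and sets the limit this way: "If persisting toxicity does not allow for the resumption of treatment after 8 weeks of delay", the patient stops study treatment.

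No section says that the 8-week denominator lengthens when Cycle 2 starts late. The weight function may be modified, but the stated ground is a different toxicity pattern by cycle, not dose delay.

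**The concern.** The weight tells the model how much of the DLT window a DLT-free patient has come through. If it reaches 1 while part of the defined window is still open, the model treats an incomplete observation as a complete one and the estimated DLT rate is too low at that moment.

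The situation can arise under the plan's own rules. Some findings that hold back a new cycle under Protocol 5.4.3 are not DLTs under 3.4: platelets below 50,000/µL without bleeding, or neutrophils below 500/µL for no more than 7 days. Such a patient is delayed, DLT-free and still in the model.

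A related gap concerns a patient who never receives dose 2, for whom 3.4 gives no window end. Protocol 9.1 has every treated patient contribute to the MTD, and in Portion B (3.3.2) only patients who stop before their first PF-05082566 dose are replaced.

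The model is still in use. Protocol 3.6 keeps entering expansion DLT data into it, and 3.3.1 and 3.3.2 attach a possible action to a DLT rate above 25%.

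**Working it through.** **Inputs.** Planned interval from dose 1 to dose 2: 28 days (Protocol 3.3.1). Window end: 28 days after dose 2 (3.4). Weight denominator: 8 weeks = 56 days (3.3.2, 9.2, SAP 5.1.2). Longest toxicity delay: 8 weeks = 56 days (5.4.3).

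**Reproducing the plan's figure.** With no delay the 3.4 window is 28 + 28 = 56 days = 8 weeks, so the texts agree.

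**With dose 2 delayed by d days.**
- Day of dose 2 = 29 + d.
- 3.4 window = 28 + d + 28 = 56 + d days.
- Share observed when the written weight reaches 1 = 56/(56 + d).
- Days from dose 2 to full weight = 56 − (28 + d) = 28 − d.

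| Delay d | Dose 2 on Day | 3.4 window (days) | Share observed | Written weight | Days from dose 2 to full weight |
|---|---|---|---|---|---|
| 7 | 36 | 63 | 0.89 | 1 | 21 |
| 14 | 43 | 70 | 0.80 | 1 | 14 |
| 28 | 57 | 84 | 0.67 | 1 | 0 |
| 56 | 85 | 112 | 0.50 | 1 | −28 |

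At d = 28, full two-cycle credit arrives on the day of dose 2. At d = 56 it arrives 28 days before dose 2, after a single dose.

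**Effect on the model.** I used the documents' power model, F = p^exp(β), with σ₀ = 0.97, the 14 example prior estimates and the posterior mean of β. I took the likelihood contribution as 1 − wF for a DLT-free patient with weight w, and F for a DLT. The patient data below are assumed, not trial data.

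1. *Active escalation.* Three DLT-free patients at each of levels 8 and 9; one DLT and three DLT-free patients at level 10. Giving those last three weight 1 instead of 0.5 lowers the estimate at level 11 from 0.263 to 0.225. The highest level at or below 25% moves from 10 to 11.
2. *Expansion, the present setting.* The 14 levels are mapped to the Portion B regular and intermediate doses from 0.03 to 5 mg/kg. There are three DLT-free patients at each regular dose, plus 20 expansion patients at 1.2 mg/kg. Four of the DLT-free patients among the 20 have the maximum toxicity delay. The estimated DLT rate at 1.2 mg/kg is:

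| DLTs among 20 | Four delayed patients at weight 0.5 | At weight 1 |
|---|---|---|
| 0 | 0.0012 | 0.0011 |
| 2 | 0.061 | 0.057 |
| 5 | 0.157 | 0.147 |

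The largest difference is 0.157 − 0.147 = 0.010, and neither column approaches 0.25.

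**The case against.** The best defence is that little is left for the error to act on. Escalation finished with no DLTs. Expansion doses are assigned by randomisation or by the sponsor (Protocol 5.1), not by the model. The action tied to the 25% limit is discretionary. The over-credit is temporary, since under either clock a patient who completes follow-up has weight 1. All of this stands, and it limits the size of the point. It does not remove the mismatch, because the model is still updated while patients are inside their windows.

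The gloss that 8 weeks means two cycles shows that the authors had the undelayed schedule in mind. That explains the mismatch without resolving it, since Protocol 5.4 lets a cycle run longer. The SAP also cites a method paper whose title mentions treatment-cycle information. Whether that method handles a late cycle cannot be judged from these documents, and neither document states such a rule.

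A reader might infer four stronger points that the documents do not support:
- *That an event after week 8 but within 28 days of dose 2 would be lost as a DLT.* Only 3.4 defines a DLT. The weight text governs patients without one, so the event still counts and tabulated DLT counts are unaffected.
- *That the Portion B clock starts with rituximab.* SAP 6.5.3.4 does note that "Cycle 1 starts on Day -7 and the first dose of PF-05082566 is scheduled for Cycle 1 Day 1", but this belongs to an exposure-delay formula. The weight text refers to cycles of PF-05082566.
- *That delayed patients are mostly those with toxicity.* No figures are given, and Protocol 5.4.2 also provides for interruptions for other reasons.
- *That Protocol 3.3.1.1 sets a competing general window.* Its wording, "can continue to be observed off study for the duration of the DLT observation period (ie, total 8 week period"), applies to Japan patients who stop after dose 2. The main 3+3 cohorts follow the 28-day rule.

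**Conclusion.** The inconsistency is real and worth correcting, but its present consequence is modest. As written, a DLT-free patient whose dose 2 is d days late receives weight 1 with 56/(56+d) of the defined window observed, falling to one half at the longest permitted toxicity delay. The result is a provisional under-estimate of the modelled DLT rate whenever the model is read before that window closes.

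In active escalation this could have changed a dose assignment, as the first assumed example shows. That phase is over with no DLTs. In the expansion cohorts the second assumed example moves the estimate by at most 0.010. Both examples rest on the documents' example prior and on invented patient data. The real size depends on how many patients had a late Cycle 2 and for how long, which is not reported.

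**What to change.** Reconcile Protocol 3.3.2 and 9.2 and SAP 5.1.2 with Protocol 3.4:
- Define the weight for a DLT-free patient as days observed since the first PF-05082566 dose, divided by the length of that patient's own 3.4 window. Assign weight 1 only when that window is complete.
- State the window end used when dose 2 is not given, and the provisional denominator used while dose 2 is overdue and its date is unknown.
- State that the clock starts at the first PF-05082566 dose in both Portions.

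The cost is wording in two protocol sections and one SAP section, plus one derived date per patient. No dose or clinical rule changes. The downside is that delayed patients reach full weight later, so the model draws less information from them in the meantime.

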3.5. MTD Definition (Portion A and Portion B)

The MTD estimate is the dose level associated with $\leq 25\%$ of patients experiencing a dose-limiting toxicity. Due to the discreteness of the dose levels and in the interest of safety of patients, the estimated MTD is the highest dose level with DLT rate closest to but no more than 0.25 per the TITE-CRM method (for Portion A in which the 3+3 design was used for PF-05082566 doses of up to 0.3 mg/kg and for Japan cohorts, the MTD estimate is the dose level at which 0/6 or 1/6 evaluable patients experience a DLT during the first two treatment cycles with the next higher dose having at least 2 of 3 to 6 patients experiencing DLTs).

3.6. RP2D (Portions A and B)

The RP2D will be chosen for further clinical development based on data for the primary and secondary endpoints of this study. Given the broad active dose range for many immunotherapies, significant clinical activity observed at lower doses will also be a factor in choosing the RP2D.

To be declared the RP2D, the MTD should also prove to be clinically feasible in a higher number of patients for long term administration. Once the MTD is identified, additional patients may be enrolled at this dosing level. In the expansion cohort, patients' DLT data will still be entered into the Bayesian statistical model of the TITE-CRM procedure. If the posterior distribution of the model incorporating the additional data from the expansion cohort suggests the estimated MTD is associated with a DLT rate, or in the case of a clear exposure plateau CCI the next lower dose or an intermediate dose level will be explored, and may be declared as the RP2D.

4. PATIENT SELECTION

This study can fulfill its objectives only if appropriate patients are enrolled. The following eligibility criteria are designed to select patients for whom participation in the study is considered appropriate. All relevant medical and nonmedical conditions should be taken into consideration when deciding whether a particular patient is suitable for this protocol.

4.1. Inclusion Criteria

Patients must meet all of the following inclusion criteria to be eligible for enrollment into the study:

1. Portion A: Histological diagnosis of advanced solid tumor malignancy or B-cell lymphoma, for which no curative therapy is available. For patients to be enrolled in the expansion cohorts:
 - Diagnosis of melanoma, renal cell carcinoma (RCC), non-small cell lung carcinoma (NSCLC), or squamous cell carcinoma of the head and neck (SCCHN);
 - Documented disease progression per RECIST v1.1 on a previous systemic immune checkpoint inhibitor therapy (anti-CTLA-4, anti-PD-1/PD-L1) administered as a single agent OR in combination;

- Measurable disease with at least 1 target lesion by RECIST v1.1 that has not been previously irradiated.
2. Portion B: Histological diagnosis of relapsed or refractory CD20-positive NHL for which no curative therapy is available, including small lymphocytic lymphoma (SLL)/chronic lymphocytic leukemia (CLL) with nodal disease (not including SLL/CLL with $>10,000$ lymphocytes/ μL , prolymphocytic leukemia, hairy cell leukemia, heavy chain disease, plasma cell myeloma, solitary plasmacytoma of bone, extraosseous plasmacytoma, lymphomatoid granulomatosis, and large B-cell lymphoma arising in Castleman disease). For patients to be enrolled in the expansion cohorts:
- Diagnosis of FL or DLBCL;
 - Measurable disease with at least 1 extranodal tumor mass >1.0 cm in the greatest transverse diameter (GTD) or in the case of malignant lymph nodes >1.5 cm in the GTD and the product of the diameters ≥ 2.25 cm² as measured by Computerized Tomography (CT) or Magnetic Resonance Imaging (MRI);
 - FL disease (Grade 1, 2, or 3a) refractory to rituximab defined as:
 - Lack of a CR or PR during a previous rituximab containing regimen comprising at least 2 doses of 375 mg/m², OR
 - Occurrence of PD within 6 months of completion of a previous rituximab containing regimen comprising at least 2 doses of 375 mg/m²
 - Treatment with ≥ 2 prior regimens for FL.
3. Availability of an archival (tissue collected within the last 6 months) OR baseline tumor biopsy (tissue collected *de novo* during the screening period); this tissue sample must be available also for a central pathology laboratory for independent review.
4. Age 18 years or older (or ≥ 20 years of age if required by local regulation).
5. Eastern Cooperative Oncology Group (ECOG) performance status of ≤ 1 .
6. Adequate bone marrow function, for Portion A defined as absolute neutrophil count (ANC) $\geq 1.5 \times 10^9/\text{L}$ ($\geq 1,500/\mu\text{L}$), platelet count $\geq 100 \times 10^9/\text{L}$ ($\geq 100,000/\mu\text{L}$), and hemoglobin >9.0 g/dL (>5.6 mmol/L), and for Portion B as ANC $\geq 1.0 \times 10^9/\text{L}$ ($\geq 1,000/\mu\text{L}$), platelet count $\geq 75 \times 10^9/\text{L}$ ($\geq 75,000/\mu\text{L}$), and hemoglobin ≥ 8.0 g/dL (≥ 5.0 mmol/L) or ≥ 8.5 mmol/L (≥ 5.3 mmol/L) for Japanese patients. In both cases, patients must be transfusion independent [ie, no blood product transfusions for a period of at least 14 days prior to enrollment (Portion B) or randomization (Portion A)].

7. Adequate Renal Function, including serum creatinine ≤ 2 x upper limit of normal (ULN) or estimated creatinine clearance ≥ 50 mL/min as calculated using the method standard for the institution.
8. Adequate Liver Function, including: a) Total serum bilirubin ≤ 1.5 x ULN unless the patient has documented Gilbert syndrome; b) Aspartate and Alanine Aminotransferase (AST and ALT) ≤ 2.5 x ULN.
9. Adequate Cardiac Function, as measured by left ventricular ejection fraction (LVEF) that is greater than 40%, or the presence of New York Heart Association (NYHA) classification of no greater than stage II congestive heart failure.
10. Resolved acute effects of any prior therapy to baseline severity or Grade ≤ 1 CTCAE v. 4.03 except for AEs not constituting a safety risk by investigator judgment.
11. Serum or urine pregnancy test (for females of childbearing potential) negative at screening. Female patients of nonchildbearing potential must meet at least 1 of the following criteria:
 - Achieved postmenopausal status, defined as follows: cessation of regular menses for at least 12 consecutive months with no alternative pathological or physiological cause;
 - Have undergone a documented hysterectomy and/or bilateral oophorectomy;
 - Have medically confirmed ovarian failure.All other female patients (including female patients with tubal ligations) are considered to be of childbearing potential.
12. Male and female patients of childbearing potential and at risk for pregnancy must agree to use two highly effective method(s) of contraception throughout the study and for at least 90 days (180 days if required by local regulation) after the last dose of assigned treatment.
13. Evidence of a personally signed and dated informed consent document indicating that the patient has been informed of all pertinent aspects of the study.
14. Willingness and ability to comply with the study scheduled visits, treatment plans, laboratory tests and other procedures.

